**Revision History:**

Protocol Version #	Description of Changes
1.0	Initial Protocol Version for IDE Submission
1.1	Minor modifications to statistical section (ITT definition, poolability definition, exploratory analysis) based on study design considerations from FDA. Other administrative changes.
2.0	Updated Sponsor contacts; section 3.2 minor clarifications on review of events; section 6.2 updated p-value; section 5.2.7 added exclusion for aspirin allergy; section 14 minor update to add reporting requirements; section 2.0 added interim analysis discussion; section 6.8 added entire section.
3.0	Updated interim analysis discussion in sections 2.0, 6.2, and 6.8. Clarified Blood Urea Nitrogen (BUN) lab requirements. Updated study document requirements in section 11.7

---

### Principal Investigator's Responsibility

Prior to participation in the BARD® LIFESTREAM™ Balloon Expandable Vascular Covered Stent (BOLSTER) Study, the Investigator must sign the Clinical Study Agreement (CSA) and obtain written approval from his/her Institutional Review Board (IRB)/Ethics Committee (EC). This approval must be in the Investigator's name and a copy sent to Bard Peripheral Vascular, Inc. ("Bard") along with the IRB/EC-approved Informed Consent Form (ICF) and the signed CSA prior to first device shipment. The Principal Investigator (PI) must receive Bard-sponsored training prior to study initiation. The PI is responsible for training all Sub-Investigators to ensure adequate training is obtained prior to performing any data collection or study-related procedures.

The Investigator must also:

- Conduct the study in accordance with the study protocol, the signed CSA, the Declaration of Helsinki, applicable national privacy laws (e.g., Health Insurance Portability and Accountability Act (HIPAA) requirements in the U.S.), applicable Food and Drug Administration (FDA), European, and International Organization for Standardization (ISO) regulations (21 Code of Federal Regulations (CFR) Parts 812, 50, 54, 56; ISO 14155:2011(E)).
- Ensure that the study does not commence until FDA and IRB/EC approvals have been obtained.
- Ensure that written informed consent is obtained from each subject prior to the conduct of any study procedure, using the current IRB/EC-approved ICF.
- Provide all required data and reports and agree to source document verification of study data with subject's medical records.
- Allow Bard personnel or their designee(s), as well as FDA representatives and other applicable authorities, to inspect and copy any documents pertaining to the study.
- Provide appropriate resources to ensure compliance with all study-related procedures and prompt submission of all electronic case report forms (eCRFs).
- Use best efforts to communicate protocol requirements to referring physicians.

The PI may delegate one or more of the above functions to a Sub-Investigator provided that the Sub-Investigator first signs the Sub-Investigator Protocol Signature Page and receives appropriate training. However, the PI retains overall responsibility for IRB/EC approval and proper conduct of the study, including obtaining and documenting the Informed Consent process, compliance with the study protocol, signed CSA, the collection of all required data, and ensuring that all study personnel have been properly trained on the protocol and have received other necessary training (if applicable) prior to performing any data collection or study-related procedures.

---

### Clinical Protocol Summary

Title:	A Prospective, Multi-Center, Non-Randomized, Single-Arm Study of the BARD® LIFESTREAM™ Balloon Expandable Vascular Covered Stent in the Treatment of Iliac Artery Occlusive Disease (BOLSTER)																																								
Sponsor:	Bard Peripheral Vascular, Inc. (“Bard”) [name]																																								
Objectives:	The objective of this study is to assess the safety and effectiveness of the LIFESTREAM™ Balloon Expandable Vascular Covered Stent for the treatment of stenoses and occlusions in the common and/or external iliac arteries.																																								
Design:	
This is a prospective, multi-center, non-randomized, single-arm clinical study of the LIFESTREAM™ Balloon Expandable Vascular Covered Stent for the treatment of stenoses and occlusions in the common and/or external iliac arteries. A composite safety and effectiveness measure of subjects receiving the BARD® Balloon-Expandable Covered Stent will be compared to a Performance Goal (PG) derived from iliac stent published literature.
 
The study will be conducted at a maximum of 35 investigational sites (“sites”) in the United States, Europe, and Australia/New Zealand.
 
Clinical follow-up for all treated subjects will be performed at hospital discharge, 30-days, and 9-, 12-, 24-, and 36-months post-index procedure. A telephone screen for all treated subjects will be performed at 6-months post-procedure.
																																								
Devices:	
The LIFESTREAM™ Balloon Expandable Vascular Covered Stent is an electropolished stainless steel balloon expandable stent encapsulated by two layers of expanded polytetrafluoroethylene (ePTFE). Size Matrix:
 
  
 Balloon Diameter (mm)	Reference Implant Length (mm)	
   
 5	16	26	37		
 
 6	16	26	37	58	
 
 7	16	26	37	58	
 
 8	16	26	37	58	
 
 9		38	58	
 
 10		38	58	
 
 12		38	58	
  
	Balloon Diameter (mm)	Reference Implant Length (mm)				5	16	26	37		6	16	26	37	58	7	16	26	37	58	8	16	26	37	58	9			38	58	10			38	58	12			38	58
Balloon Diameter (mm)	Reference Implant Length (mm)																																								
5	16	26	37																																						
6	16	26	37	58																																					
7	16	26	37	58																																					
8	16	26	37	58																																					
9			38	58																																					
10			38	58																																					
12			38	58																																					
Enrollment:	
Enrollment will continue until one-hundred fifty-four (154) subjects are treated with the LIFESTREAM™ Balloon Expandable Vascular Covered Stent, which is an estimated three-hundred eight (308) consecutive subjects in a non-randomized fashion.
 
Subjects will be considered enrolled in the study at the time the informed consent document is signed (an estimated 308 subjects). After the subject has met all eligibility criteria, undergone successful PTA of the target lesion(s), and the LIFESTREAM™ Balloon Expandable Vascular Covered Stent catheter is introduced (i.e. delivery system enters the subject’s body), the subject will enter the primary analysis population (up to 154 subjects).
																																								

Investigational Sites:	Up to thirty-five (35) sites will be utilized for this study throughout the United States (U.S.), Europe, and Australia/New Zealand.
Study Population:	Subjects will be males or non-pregnant females, at least 21 years of age, with an expected lifespan sufficient to allow for completion of all study procedures. Eligible subjects will have intermittent claudication or ischemic rest pain and angiographic confirmation of either de novo or restenotic (non-stented) lesion(s) $\geq 50\%$ in the common and/or external iliac arteries.
Eligibility Criteria:	
Inclusion Criteria
 
Clinical Inclusion Criteria
 
 
1. The subject provides written informed consent using an Informed Consent Form (ICF) that is reviewed and approved by the Ethics Committee (EC) / Institutional Review Board (IRB) for the site.
 
2. Subject agrees to comply with the protocol-mandated follow-up procedures and visits.
 
3. The subject is a male or non-pregnant female <math>\geq 21</math> years old with an expected lifespan sufficient to allow for completion of all study procedures. Female subjects of childbearing potential must have a negative pregnancy test (urine or blood) within 14 days prior to the index procedure.
 
4. The subject has intermittent claudication (Rutherford Category 2-3) or ischemic rest pain (Rutherford Category 4).
 
5. The subject is able and willing to comply with any required medication regimen.
 
 
Angiographic Inclusion Criteria
 
 
6. The subject has evidence of single, bilateral, or multiple de novo and/or restenotic (non-stented) lesion(s) in the native common and/or external iliac artery that is (are) <math>\geq 50\%</math> stenosed (including total occlusions) as determined by the Investigator's visual estimate.
 
7. The target lesion(s) can be successfully crossed with a guide wire and pre-dilated with an appropriately sized PTA balloon. Devices such as chronic total occlusion (CTO) catheters or re-entry devices may be used to facilitate target lesion(s) crossing.
 
8. The reference vessel diameter(s) is (are) between 4.5 mm and 12.0 mm in diameter as determined by the Investigator's visual estimate.
 
9. The target lesion(s) is (are) <math>\leq 100</math> mm in combined length (per side) as determined by the Investigator's visual estimate.
 
10. The subject has angiographic evidence of a patent (<math>< 50\%</math> stenosis) profunda and/or superficial femoral artery (SFA) in the target limb(s) as determined by the Investigator's visual estimate.
 
 
Ipsilateral and contralateral SFA lesions may be treated before or after target lesion treatment, considering the following criteria are met:
 
 
- <math>\geq 50\%</math> stenosis
 
- Stenosis(es) <math>\leq 15</math>cm in total length or a Total Occlusion <math>\leq 5</math>cm in length
 
- <math>\geq 1</math> vessel run-off
 


- No thrombus or severe calcification
- Use of on-label devices

Contralateral iliac lesions (not meeting study eligibility criteria) may be treated at the discretion of the investigator with on-label (non-investigational) devices at the time of the index procedure. Other planned interventions must take place 30 days before the index procedure or after 30 days post-index procedure.

### **Exclusion Criteria**

[figure not shown]
[figure not shown]

#### **Clinical Exclusion Criteria**

1. The subject is unable or unwilling to provide written informed consent, or is unable or unwilling to conform to the study protocol follow-up procedures and visits.
2. The subject is or plans to become pregnant during the study.
3. The subject is asymptomatic, has mild claudication or critical limb ischemia with tissue loss described as Rutherford Category 0 (asymptomatic), 1 (mild claudication), 5 (minor tissue loss), or 6 (major tissue loss).
4. The subject has a vascular graft previously implanted in the native iliac vessel.
5. The subject suffered a hemorrhagic stroke or transient ischemic attack (TIA) within 3 months prior to the index procedure.
6. The subject has a known uncorrectable bleeding diathesis or active coagulopathy (platelet count < 80,000/ $\mu$ L).
7. The subject has a serum creatinine  $\geq$  2.5 mg/dl or is currently on dialysis.
8. The subject has a known allergy or sensitivity to stainless steel (i.e., Nickel), ePTFE, or has intolerance to the antiplatelet, anticoagulant or thrombolytic medications required per the protocol.
9. The subject has a known allergy or sensitivity to contrast media, which cannot be adequately pre-medicated.
10. The subject had a prior vascular intervention(s) within 30 days before, or has an intervention planned for within 30 days after the index procedure. Refer to inclusion criterion #10 for exceptions on SFA lesions and contralateral iliac lesions.
11. The subject has another medical condition, which, in the opinion of the Investigator, may cause him/her to be non-compliant with the protocol, confound the data interpretation, or is associated with a life expectancy insufficient to allow for the completion of study procedures and follow-up.
12. The subject is currently participating in an investigational drug, biologic, or another device study. Studies requiring extended follow-up for products that are now commercially available are not considered investigational studies.

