
Secondary Endpoints:
	
 
– The rate of Major Adverse Events (MAE) defined as device and/or procedure-related death or MI through 30 days, or any TLR or target limb(s) major amputation through 9-months post-index procedure.
 
– Acute Lesion Success defined as attainment of < 30% residual stenosis of the target lesion after the index procedure using any percutaneous method and/or non-investigational device (i.e., post-dilatation).
 
– Acute Procedure Success defined as lesion success and no periprocedural complications (death, stroke, myocardial infarction (MI), emergent surgical revascularization, significant distal embolization in target limb, and thrombosis of target vessel) prior to hospital discharge.
 
– Acute Technical Success defined as successful deployment of the LIFESTREAM™ Balloon Expandable Vascular Covered Stent at the intended location.
 
– Target Lesion Revascularization (TLR) at 6-, 9-, 12-, 24-, and 36-months post-index procedure.
 
– Target Vessel Revascularization (TVR) at 6-, 9-, 12-, 24-, and 36-months post-index procedure.
 
– Sustained Clinical Success at 30-days and 9-, 12-, 24-, and 36-months post-index procedure.
 
– Primary Patency at 9-, 12-, 24- and 36-months post-index procedure corresponding to PSVR ≤ 2.4.
 
– Primary Assisted Patency at 9-, 12-, 24-, and 36-months post-index procedure corresponding to PSVR ≤ 2.4.
 
– Secondary Patency at 9-, 12-, 24-, and 36-months post-index procedure corresponding to PSVR ≤ 2.4.
 
– Quality of Life at baseline, 30-days and 9-, 12-, 24- and 36-months post-index procedure.
 

Lead Principal Investigator:
	
[name]  

Angiographic Core Lab:
	

Duplex Ultrasound Core Lab:
	

Please refer to Site Contacts List for all Sponsor, Investigator, and Vendor contact information.

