##### **Clinical Inclusion Criteria**

1. The subject provides written informed consent using an Informed Consent Form (ICF) that is reviewed and approved by the Ethics Committee (EC) / Institutional Review Board (IRB) for the site.
2. Subject agrees to comply with the protocol-mandated follow-up procedures and visits.
3. The subject is a male or non-pregnant female  $\geq 21$  years old with an expected lifespan sufficient to allow for completion of all study procedures. Female subjects of childbearing potential must have a negative pregnancy test (urine or blood) within 14 days prior to the index procedure.
4. The subject has intermittent claudication (Rutherford Category 2-3) or ischemic rest pain (Rutherford Category 4).
5. The subject is able and willing to comply with any required medication regimen.

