#### 4.3.2. Exclusion Criteria

A subject must be excluded if any of the following criteria are met:

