##### Clinical Exclusion Criteria

1. The subject is unable or unwilling to provide written informed consent, or is unable or unwilling to conform to the study protocol follow-up procedures and visits.
2. The subject is or plans to become pregnant during the study.
3. The subject is asymptomatic, has mild claudication or critical limb ischemia with tissue loss described as Rutherford Category 0 (asymptomatic), 1 (mild claudication), 5 (minor tissue loss), or 6 (major tissue loss).
4. The subject has a vascular graft previously implanted in the native iliac vessel.
5. The subject suffered a hemorrhagic stroke or transient ischemic attack (TIA) within 3 months prior to the index procedure.
6. The subject has a known uncorrectable bleeding diathesis or active coagulopathy (platelet count  $< 80,000/\mu\text{L}$ ).
7. The subject has a serum creatinine  $\geq 2.5$  mg/dl or is currently on dialysis.
8. The subject has a known allergy or sensitivity to stainless steel (i.e., Nickel), ePTFE, or has intolerance to the antiplatelet, anticoagulant or thrombolytic medications required per the protocol.
9. The subject has a known allergy or sensitivity to contrast media, which cannot be adequately pre-medicated.

10. The subject had a prior vascular intervention(s) within 30 days before, or has an intervention planned for within 30 days after the index procedure. Refer to inclusion criterion #10 for exceptions on SFA lesions and contralateral iliac lesions.
11. The subject has another medical condition, which, in the opinion of the Investigator, may cause him/her to be non-compliant with the protocol, confound the data interpretation, or is associated with a life expectancy insufficient to allow for the completion of study procedures and follow-up.
12. The subject is currently participating in an investigational drug, biologic, or another device study. Studies requiring extended follow-up for products that are now commercially available are not considered investigational studies.

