#### **5.1.6. Procedural Medications**

During the index procedure, it is recommended that subjects receive intravenous (IV) heparin or bivalirudin, as per the institutional standard of care. If the subject is not currently taking clopidogrel, a loading dose of 300 mg – 600 mg (oral) should be administered at the time of the index procedure, or immediately following successful intervention. Ticlopidine may be administered if the subject has an allergy or contraindication to clopidogrel. Clopidogrel is not required if a subject is taking warfarin, prasugrel, ticagrelor, and/or approved direct thrombin inhibitors (e.g., dabigatran) or factor Xa inhibitors (e.g., rivaroxaban, apixaban). The total amount of heparin (bivalirudin) or clopidogrel (ticlopidine) that is administered during the index procedure should be documented.

If the subject is diabetic, it should be documented whether the subject is on insulin, oral agents, or a dietary regiment for treatment.

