### 5.2.7. Post-Procedure Medications

Treated subjects are to receive a minimum of 75 mg of ASA orally per day for a minimum of 6 months, and a minimum of 75 mg of clopidogrel orally per day for a minimum of 3 months. Subjects should be excluded if they have an allergy to aspirin at baseline. Ticlopidine may be prescribed if the subject has an allergy or contraindication to Clopidogrel. Clopidogrel is not required if a subject is taking warfarin, prasugrel, ticagrelor, and/or approved direct thrombin inhibitors (e.g., dabigatran) or factor Xa inhibitors (e.g., rivaroxaban, apixaban); however the subject should receive a minimum of 75 mg of ASA orally per day for a minimum of 6 months. Investigators may elect to use additional anticoagulants, for example, low molecular weight heparin as they deem medically appropriate. If the treated subject requires subsequent surgery that necessitates the discontinuation of these medications, then the subject is to resume protocol required medications as soon as possible after the medical procedure.

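### Exclusion 5 bars a recent TIA or hemorrhagic stroke by rule but not a completed ischemic stroke, which the other criteria reach only in part

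*Combined protocol and SAP*

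**What the plan says.** Exclusion 5 appears twice, in the Clinical Protocol Summary and in section 4.3.2, with the same words: "The subject suffered a hemorrhagic stroke or transient ischemic attack (TIA) within 3 months prior to the index procedure". Section 4.3.2 makes the list mandatory: "A subject must be excluded if any of the following criteria are met". No inclusion or exclusion criterion names ischemic stroke, or stroke without a qualifier.

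The other criteria that could reach such a patient are these:

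- Exclusion 10: "The subject had a prior vascular intervention(s) within 30 days before, or has an intervention planned for within 30 days after the index procedure". It has stated exceptions for superficial femoral artery (SFA) and contralateral iliac lesions.
- Exclusion 11, which leaves to judgment a patient with "another medical condition, which, in the opinion of the Investigator, may cause him/her to be non-compliant with the protocol, confound the data interpretation", or with too short a life expectancy.
- Inclusion 5: "The subject is able and willing to comply with any required medication regimen".
- Exclusion 6 (clotting disorders), exclusion 8 (allergy to device materials or intolerance of the required antithrombotic drugs) and inclusion 3 (adequate expected lifespan).

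On treatment, section 5.1.6 states that "it is recommended that subjects receive intravenous (IV) heparin or bivalirudin". Section 5.2.7 requires aspirin for at least 6 months and "a minimum of 75 mg of clopidogrel orally per day for a minimum of 3 months", with listed alternatives to clopidogrel.

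As an outcome, stroke before discharge is one of the complications that defeat Acute Procedure Success (section 3.2): "death, stroke, myocardial infarction (MI), emergent surgical revascularization", among others. Section 6.4 treats that endpoint descriptively.

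**The concern.** A TIA is the transient form of cerebral ischemia. Exclusion 5 bars the transient event and leaves the completed one to judgment. Bleeding risk could explain listing hemorrhagic stroke alone, but it does not explain adding TIA, and the protocol gives no reason.

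Two things are at stake. The first is safety: a patient with a recent ischemic stroke may have an arterial procedure with antithrombotic treatment although no rule has addressed that history. The second is consistency. With up to 35 sites, some investigators may read the criterion literally and others as meaning any recent stroke. The per-protocol set inherits the difference, because section 6.1 removes subjects with eligibility deviations. A subject treated despite a recent TIA would leave that set, and one with a recent ischemic stroke would stay.

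**Working it through.** **Step 1: does any other criterion close the gap?** Take a patient with an ischemic stroke in the 3 months (about 90 days) before the procedure.

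| Criterion | What it reaches | What it leaves |
|---|---|---|
| Exclusion 5 | Hemorrhagic stroke, TIA | Completed ischemic stroke |
| Exclusion 10 | Any vascular intervention in the 30 days before, or planned in the 30 days after, whatever its cause, apart from the stated exceptions | Strokes managed medically; interventions on days 31-90 |
| Exclusion 11 | Strokes the Investigator thinks threaten compliance, interpretation or survival | Strokes with good recovery; procedural and bleeding risk are not among its grounds |
| Exclusions 6 and 8, inclusions 3 and 5 | Individual patients with a clotting disorder, drug intolerance, short lifespan or inability to follow the medication | The condition as such |

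The look-back of exclusion 10 is 30/90, or one third, of that in exclusion 5. What remains is mainly a medically managed ischemic stroke, or one treated by intervention on days 31-90, without a deficit that triggers exclusion 11.

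**Step 2: the plan's own figures.** The plan has no figure for this point. Its consent estimate follows from 154 treated subjects and 50% screen failure (sections 5.2.2 and 6.7): 154/(1 - 0.5) = 308. Its evaluable sample size of 139 also reproduces. With an exact one-sided binomial test of 19.5% against 10.5%, success at n = 139 is 19 or fewer events, with alpha 0.0474 and power 0.9087. None of these inputs depends on exclusion 5.

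**Step 3: how many subjects.** The documents give no prevalence, so every rate below is an assumption.

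- Ischemic stroke in the prior 3 months among otherwise eligible subjects, 0.5-2%: 154 × 0.005 = 0.77 to 154 × 0.02 = 3.08 subjects.
- Other criteria already remove 25-75% of them: 0.77 × 0.25 = 0.19 to 3.08 × 0.75 = 2.31 subjects remain.

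**Step 4: effect on Acute Procedure Success.** Assume that stroke risk before discharge is 0.5-9 percentage points higher than in the subjects who would replace them.

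- Excess strokes in the whole study: 0.19 × 0.005 = 0.001 to 2.31 × 0.09 = 0.21.
- Shift in the endpoint: 100 × 0.00096/154 = 0.0006 points to 100 × 0.208/154 = 0.135 points.
- For scale, one actual stroke is 100/154 = 0.65 points.

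**Step 5: extra consents if the criterion is widened.**

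- If none of these subjects is already excluded: 308/0.995 - 308 = 1.5 to 308/0.98 - 308 = 6.3.
- If 25-75% already are, the newly excluded share is 0.005 × 0.25 = 0.00125 to 0.02 × 0.75 = 0.015: 308/(1 - 0.00125) - 308 = 0.4 to 308/(1 - 0.015) - 308 = 4.7.

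**Step 6: the primary endpoint and MAE.** Neither lists stroke. Both count a death related to the device or procedure within 30 days (sections 3.1 and 3.2). A stroke enters them only if it is fatal, so related, and within that period.

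**The case against.** The strongest reply is that the asymmetry rests on a clinical premise, that a recent ischemic stroke is at least as disqualifying as a TIA. The documents give no stroke risk by history and no guidance on timing. Matching words in two places look chosen rather than mistyped. The obvious hazard of the required drugs is bleeding, and exclusions 5, 6 and 8 already address that. Exclusion 11 is broadly worded and has no time limit: a stroke that affects gait could well confound the walking questionnaire and the Rutherford category. The magnitude is assumed throughout, and even its upper end is about 0.21 excess strokes.

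Much of this stands. Intent is unknown, no harm is demonstrated, and the drug regimen is weak support for the change. It does not remove the inconsistency, because no criterion bars a well-recovered, medically managed ischemic stroke while a TIA in the same window is barred outright.

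A reader might infer two stronger claims. One is that recent ischemic stroke patients are admitted freely. The partial cover in step 1 contradicts that. The other is that the trial's results are compromised. The documents do not support that either, since stroke reaches the primary endpoint and MAE only through a related death within 30 days.

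**Conclusion.** The point holds as a low-severity improvement in safety and screening consistency. Exclusion 5 yields an incoherent rule, and the other criteria narrow the gap without closing it.

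Few subjects are likely to be affected: about 0.2-2.3 of 154, given the assumed 0.5-2% prevalence and 25-75% overlap. That range measures exposure, not harm. The direct effect on results is confined to Acute Procedure Success, at 0.0006-0.135 points under the further assumption of 0.5-9 points of excess risk. The primary endpoint and MAE are not wholly insulated, but the route to them is narrow. Sample size, performance goal and p-value thresholds stand as written.

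**What to change.** In the Clinical Protocol Summary and in section 4.3.2, replace the events named in exclusion 5 with *any stroke (ischemic or hemorrhagic) or transient ischemic attack (TIA)*, and keep the 3-month window. Bring the eligibility eCRF item into line; the form is not in the documents. Apply the change only to subjects still to be enrolled.

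The text change is small, but the cost is more than the phrase. It needs an amendment to an IDE protocol already at version 3.0, IRB/EC handling, and notice to or retraining of up to 35 sites. It adds a few screen failures: about 0.4-4.7 consents on top of 308 if other criteria already remove 25-75% of these subjects, and at most about 6 if they remove none. Folding the change into the next amendment would keep the cost down. The documents do not say whether enrollment is still open, and if it has closed the change brings no benefit.
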